**In Vivo Evaluation of Antibacterial Toothpaste Efficiency and Patients' Satisfaction:
a Double-blind Randomised Controlled Trial**

NCT05569850

November, 20th 2024

Study Protocol

This was a single-site, double-blind RCT that was conducted in the Dental Clinic of Bologna University (DIBINEM), Bologna, Italy in the period from November 2022 until July 2023. Before initiating the trial, the study protocol was reviewed and approved by the University Ethics Committee (793/2022/SPER/AUSLBO). The trial was in accordance with Helsinki Declaration of Human Rights [21] and followed the CONSORT statement. The tested dentifrices included a newly introduced ZCT-, HAP- and KCit- 1450 ppm sodium monofluorophosphate containing (Experimental group; Mentadent PROTECT+ Carie, Mentadent, Unilever, Milan, Italy) and 1450 ppm NaF containing (Control group; AZ Multi-Protezione Scudo Protettivo Famiglia) toothpastes.

Sample size, recruitment and eligibility criteria

The number of patients was determined based on the power analysis performed using data from a previously published study in order to assure a power of 80% for finding the statistically significant differences given the standard value of type I errors (0.05). Based on the outcomes of the power calculation (effect size $f=0.2291667$, at the level of α 0.05, and $1-\beta$ prob 0.80), the determined sample size was 92 patients. Considering the probability of loss to follow-up 10% of the minimum size per group was added, leading to the final sample size of 100 patients.

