During the baseline visit, all patients completed a custom-made questionnaire (supplementary file) containing questions regarding dental sensitivity ("self-reported" sensitivity), their perception of tooth color and overall perception of the toothpaste they were using at the time. Subsequently, they were asked to collect 2 ml of unstimulated saliva in sterile tubes (Greiner centrifuge tube, Sigma-Aldrich, St Louis, MO, USA). Saliva was immediately processed for microbiological analysis as thereafter described. Upon saliva collection, a sensitivity test was conducted by applying a tactile and air-stimulus (duration: 2 s, distance from the tooth surface: 1 cm) test to all teeth of the four quadrants. The subjects' response was recorded on a 4-point Schiff Sensitivity Scale [25] and visual-analogue scale, respectively. Additionally, plaque index (Modified Quigley and Hein) was scored on a 6 point scale at 3 buccal and 3 lingual sites per tooth after it had been disclosed with a disclosing agent (Biofilm Disclosure, EMS Dental, Nyon, Switzerland); gingival index according to Löe-Silness was also recorded, as well as bleeding on probing index. Patients' tooth color was determined under daily light using the Vita classical shade guide. Finally, at the end of the baseline visit, the participants were provided with the same soft-bristled toothbrush (Mentadent P, Mentadent, Unilever) and randomly assigned into one of the two groups (n=50) according to the dentifrice used. An online software (<https://www.sealedenvelope.com>) was utilized for randomization purposes by a staff member unaware of the study protocol. In order to enable complete blinding of the participants and dental examiner to the group assignment, the two dentifrices were distributed in identical plain white tubes provided with only letters A or B, with no other visible marks. The patient's code and dentifrice assigned (A or B) were documented in the chart for later reference. From the baseline visit, the subjects had to restrain from using any other products or means of oral hygiene except those provided and were invited to follow the domiciliary oral hygiene instructions as previously described. In case of any adverse events were to occur, the subjects were advised to discontinue the use of the toothpaste and were withdrawn from the study. The 4 weeks follow-up visit was fixed (recall).

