After 4 weeks (recall), the patients returned to the study site for a final visit after having abstained from brushing or eating at least 5 hours before the visit. During this visit, the patients were asked to fill in the questionnaire (supplementary file), while the saliva collection and all clinical procedures described above were repeated by the same dentist.

Microbiological procedures

The saliva collected during the baseline and recall visits was processed for microbiological analysis within 3 hours of sample acquisition. Briefly, 0.1 ml of saliva was diluted in 9.9 ml of sterile phosphate-buffered saline solution until 10^{-8} was reached. Subsequently, the diluted samples were dispersed on Mitis Salivarius Selective Agar (MSB, Microbiol Diagnostici, UTA, CA, Italy) and the plates were incubated at 37°C for the next 48-72h. The bacterial colonies were identified by morphology and counted by one trained investigator, blinded to the groups. *S. mutans* colonies (CFU) were multiplied by their respective dilution ratio to calculate the number of colonies per one milliliter

(CFU/mL) of each subject's saliva sample. In order to perform statistical analysis, a base-10 logarithm transformation was applied to the calculated CFU/ml values.

Statistical analysis

After checking the normality (Kolmogorov-Smirnov) and the homoscedasticity (modified Levene's test) of the data, the Two Way Repeated Measures ANOVA (One Factor Repetition) followed by Bonferroni post-hoc were run to investigate the effect of the tested dentifrices on salivary counts of *S. mutans*, as well as plaque and gingival indexes. Since the data retrieved from questionnaires were not normally distributed (Kolmogorov-Smirnov, $p<0.05$), the non-parametric Mann-Whitney U-test was run. All analyses were performed by a statistician blinded to the groups using SigmaPlot 14.0 (Systat Software, Chicago, IL, USA). In all tests, the significance level was set at $\alpha=0.05$.

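### No primary outcome is named and three efficacy outcomes are each tested at 0.05, so the chance of a false between-arm finding is about 11–14% rather than 5%, unless a primary was prespecified elsewhere

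*Combined protocol and SAP*

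**What the plan says.** - **Outcomes tested.** The Statistical analysis section lists salivary *S. mutans* counts, "as well as plaque and gingival indexes", under one method and without ranking them. No outcome is called primary or secondary anywhere in the document.
- **Method.** The ANOVAs are "followed by Bonferroni post-hoc were run to investigate the effect of the tested dentifrices". The section does not say whether the group term or the group-by-visit term carries the dentifrice comparison.
- **Level.** "In all tests, the significance level was set at" 0.05. This also covers the Mann-Whitney tests on the questionnaires, whose items are in a supplementary file not included here.
- **Sizing.** The sample size section uses one type I error of 0.05, 80% power and f = 0.2291667 from a published study, and concludes that "the determined sample size was 92 patients". It does not say which outcome f describes.
- **Timing.** Before the trial began, "the study protocol was reviewed and approved by the University Ethics Committee"; the document does not say whether that protocol named a primary. The trial ran from November 2022 to July 2023, this document is dated November 2024, and it already reports a finding from the data ("Since the data retrieved from questionnaires were not normally distributed").

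**The concern.** A 5% error rate applies to one test. With three unranked outcomes at 0.05 each, a reader who sees one significant result cannot attach 5% to it, because any of the three could have produced it. The Bonferroni step can be mistaken for protection here. As written, it handles comparisons after an ANOVA, and nothing says it spans the three ANOVAs.

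The sizing does not settle the matter, since f is attached to no outcome. Nor can the gap be closed by naming a primary now: the data are in and have been examined, so a first-time choice would be made with knowledge of the results.

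**Working it through.** **Inputs from the document.** Three ANOVA outcomes and α = 0.05 per test (Statistical analysis); f = 0.2291667, power 0.80, N = 92, so 46 per arm (sample size section). **Assumed:** correlations between outcomes and between visits, since none is given.

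**1. Does the sizing point to a primary outcome or a tested term?** The printed inputs alone do not give 92.
- As a plain two-group ANOVA, this f needs 152 in total.
- For the repeated-measures group term with two visits, noncentrality is f²·N·2/(1+ρ). At an assumed visit correlation ρ = 0.2 this is 0.0525 × 92 × 2/1.2 = 8.05, and power is 80.2%.
- For the group-by-visit term, 62 in total suffice at ρ = 0.2 and 40 at ρ = 0.5.

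The stated 92 can therefore be reached only with a visit correlation and a tested term that the document does not give. It identifies neither outcome nor term.

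**2. Three tests, no adjustment.** If independent: 1 − 0.95³ = 1 − 0.8574 = 0.1426. Under any dependence, at most 3 × 0.05 = 0.15.

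**3. Correlated tests.** For three two-sided normal tests with common correlation ρ and c the two-sided critical value:

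P(any) = 1 − ∫ φ(u) [Φ((c − √ρ·u)/√(1−ρ)) − Φ((−c − √ρ·u)/√(1−ρ))]³ du

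Holm makes at least one rejection exactly when the smallest p is at or below 0.05/3 = 0.0167. With all three nulls true, its error is the same formula at that level.

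| Correlation (assumed) | Any of three at 0.05 | With Holm |
|---|---|---|
| 0 | 14.3% | 4.9% |
| 0.3 | 13.6% | 4.8% |
| 0.5 | 12.5% | 4.5% |
| 0.7 | 10.9% | 3.9% |
| 0.8 | 9.8% | – |
| 0.9 | 8.4% | – |

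If only plaque and gingival indexes are closely related (0.7) and *S. mutans* is weakly related to both (0.2), the unadjusted figure is 12.8%.

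**4. Check by simulation.** In 60,000 null trials with 46 per arm and visit correlation 0.5, the unadjusted error at outcome correlations 0/0.3/0.5/0.7 was 14.3/13.7/12.5/11.0% for baseline-adjusted tests and 14.4/13.7/12.6/10.9% for the group-by-visit term. Holm gave 4.0–5.0% and 4.0–5.1%.

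**5. If both ANOVA terms may support a claim.** Treating the two terms as independent (equal variance at both visits), the error is 1 − (1 − P)²: 26.5% at correlation 0, falling to about 21% at 0.7. Counting questionnaire tests would raise it further.

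**6. Power cost of Holm, 46 per arm.** The worst case is a test at 0.0167.

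| Reading of the effect | at 0.05 | at 0.0167 |
|---|---|---|
| Effect back-solved to give 80% (d = 0.590) | 80% | 65% |
| f as two-group effect, d = 2f = 0.458, unadjusted t test | 58% | 41% |
| Same d, baseline-adjusted, baseline-to-recall r = 0.3/0.5/0.7 | 63/71/86% | 45/54/74% |
| Same d, group-by-visit (change), r = 0.3/0.5/0.7 | 45/58/80% | 29/41/65% |
| f as repeated-measures interaction effect, visit correlation 0/0.2/0.5 | 87/93/99% | 75/85/97% |

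The document does not say which reading of f applies.

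**The case against.** - **The prespecification may exist elsewhere.** The text is in the past tense, refers to a protocol approved before the trial, and carries a registration number. Its silence is weak evidence that no primary was ever named. This stands as a limit: what is certain is that this document names none and gives no rule across outcomes. A dated registration entry made before the data would serve as well as the approved protocol.
- **The range depends on assumptions.** The 11% end comes from stopping at a correlation of 0.7; beyond that the figure drops below 10%. This is fair, but even at 0.9 it is 8.4%, and counting both ANOVA terms or the questionnaires moves it the other way.
- **No rule says that any one positive result is enough.** If the outcomes are separate descriptive questions, familywise control is a matter of convention. This also stands as a condition: the figures apply when a single significant result supports an efficacy claim. The document does not rule that out.
- **Changing the model is not needed for multiplicity control.** Correct. Holm on the group-by-visit term controls the error equally well. Baseline adjustment is preferred for power, and a change made now must be disclosed too.
- **The power loss may be overstated.** If f is an interaction effect, power remains 75% or more at 0.0167 in the cases shown. The document does not settle this.

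**Conclusion.** The concern holds. As written, the analysis has three unranked outcomes at 0.05 each and no control across them. With one between-arm test per outcome, the chance of at least one false difference is about 11–14% for assumed correlations from 0.7 down to 0, and at most 15% under any dependence, against the single 5% used for sizing.

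This rests on two conditions: any one of the three may support a claim, and no primary was prespecified in a source not included here. Confidence is high about what the document omits and lower about the exact error rate, because the correlations and the tested term are not given. It should be corrected, and doing so is cheap.

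**What to change.** 1. **One test per outcome.** For each of *S. mutans*, plaque index and gingival index, use the 4-week between-arm difference adjusted for the baseline value already collected. If the stated ANOVA is kept, use only its group-by-visit term.
2. **Control across the three.** Apply Holm at a familywise two-sided 0.05: the smallest p-value against 0.0167, the next against 0.025, the last against 0.05, stopping at the first that fails.
3. **State the source.** If the approved protocol or a registration entry dated before the data named a primary outcome, cite it, test that outcome alone at 0.05 and report the other two as secondary. If not, say that none was prespecified and that the Holm rule, and any change of model, came after the data.
4. **Label the rest.** Report questionnaire items and the other measures with 95% confidence intervals, marked as not multiplicity-controlled.

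**Cost.** Three models rerun on existing values, plus wording. An outcome that truly had 80% power at 0.05 would fall to about 65% in the worst case; baseline adjustment can recover part of that, depending on how strongly baseline predicts recall.
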